**Figure 2. Hypothetical Data Illustrating the Primary Hypothesis**

#### 11.1.2 Secondary Hypothesis

- We hypothesize that among this study population of participants with TMD, the efficacy of propranolol will vary according to the number of LPS haplotypes of the COMT gene.
- We hypothesize that, compared with participants in the placebo-treated arm, participants in the propranolol-treated arm will have more favorable secondary endpoints, namely: (1) reduction in additional ratings of pain; (2) reduction in examiner-assessed levels of

pain sensitivity (pressure and heat pain sensitivity); (3) better participant ratings of physical function, emotional function, and global improvement; and (4) less frequent use of rescue medications and over-the-counter medications for pain.

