#### **11.4.2 Analysis of the Secondary Hypotheses**

To test the secondary hypothesis of gene-by-treatment interaction, the linear mixed model described for the primary analysis will be extended by adding three sets of predictor variables: (1) the number of COMT LPS haplotypes (0, 1, or 2) will be modeled as a fixed effect, either as a continuous variable, or as a 3-level categorical variable (i.e., two dummy variables), with the decision based on the approach that optimizes model fit, as determined by Akaike's Information Criterion; (2) two-way interactions between haplotype effect and treatment allocation and between haplotype effect and visit sequence; and (3) a three-way interaction term between the

---

haplotype effect, treatment allocation, and visit sequence. The gene-by-treatment interaction at V4 is the interaction of interest.

For descriptive purposes, an analogous model will generate efficacy estimates according to COMT ValMet genotype as the genetic marker instead of the number of LPS haplotype. In an analogous manner, the genotype will be coded either as a continuous or categorical variable based on optimal model fit. Efficacy estimates will be calculated for descriptive purposes only; there will be no hypothesis tests for the interaction terms.

Another descriptive set of secondary analyses will adapt the approach for analysis of the LPS haplotype, restricting the model to non-Hispanic whites. This is consistent with the approach of some genetic researchers who advocate racial-group restriction as a preferable analytic method to control for population stratification.

Linear mixed models will be used to evaluate effects of treatment group allocation on secondary efficacy variables (see Statistical Analysis Plan for full details).

Linear regression or other appropriate statistical modeling will evaluate the effects of treatment on the number of days in which rescue medications for TMD-related pain reportedly were used and on the number of days in which over-the-counter analgesics (namely, NSAIDs, acetaminophen, and aspirin) reportedly were used for treatment of any type of pain.

See the Statistical Analysis Plan for more details on these secondary analyses.

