2.1.2 Secondary Objectives

The secondary objectives are:

• To investigate gene-by-treatment group interaction to determine whether the efficacy of extended-release propranolol in the reduction of the pain index varies according to participants' polymorphisms in the coding region of the *COMT* gene.

Version 3.0 Page 5 of 25

• To investigate the efficacy of extended-release propranolol compared with placebo using secondary endpoints: additional pain ratings; examiner assessments of experimental pain sensitivity; participant ratings of physical function, emotional function, global impression of change; occurrence of symptoms and AEs; and use of rescue medications.

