	The count of examination familiar pain masticatory structure locations will be computed (range=0 to 8) representing places in which pain is elicited during jaw provocation during the examination: temporalis muscles, masseter muscles, other masticatory muscles, and TMJs, each reported bilaterally, and confirmed by the subject to be familiar to pain experienced in the prior 30 days (Items 4, 5 and 6 of DC/TMD form). Jaw provocation includes jaw mobility maneuvers and standardized pressure palpation.
Vital signs	For each visit when it was measured, systolic and diastolic blood pressure (recorded in mmHg) and heart rate (recorded in beats per minute) will be computed, each as the mean of three repeated measurements taken 2 min apart and recorded as Vital Signs in RAVE.
Subjective health status (SF-12v2 questionnaire)	For each visit when it was administered, published scoring algorithms will be used to compute two continuous variables from the SF-12v2 questionnaire: a) Physical Component Subscale and b) Mental Component Subscale (SF-12v2 questionnaire).
Headache Impact (HIT-6 questionnaire)	For each visit when it was administered, published scoring algorithms will be used to compute the Total Score for headache impact, a continuous variable.
Graded chronic pain ratings (GCPS questionnaire)	For each visit when it was administered, published scoring algorithms will be used to compute two continuous measurements (Characteristic Pain Intensity and Pain Interference) and one derived ordinal score (Grade of Chronic Pain) from the GCPS questionnaire.

Version 3.0 Page 13 of 25

Efficacy Variables	Description and Derivation
Anxiety and Depression (HADS questionnaire)	For each visit when it was administered, published scoring algorithms will be used to compute two continuous measurements: Anxiety, and Depression scores.
Patient global impression of change (PGIC questionnaire)	The ordinal rating of change, measured at the subject's visits 3 and 4, will be reported as two secondary outcome variables.
Subjective measure of jaw functional limitation (JFLS questionnaire)	For each visit when it was administered, published scoring algorithms will be used to compute four continuous scores of subjective jaw function from the JFLS questionnaire: a) Chewing Limitation b) Opening Limitation; c) Verbal & Emotional Expression Limitation; and d) Combined Global Measure.

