8.3 Analysis Methods

The ITT population will be used in all analyses unless otherwise stated. The alpha level for determining significance will be set to 0.05 for all inference tests. The mixed models analyses described below automatically adjust for missing values; there will be no further imputation or adjustments for missing values. During the analysis of the primary hypothesis, treatment allocation will be masked (i.e., groups will be labeled A and B) during the statistical programming and unmasked only after the statistical programming code has been finalized.

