8.3.2 Secondary Efficacy Analyses

For secondary efficacy measures that are continuous variables or counts (Table 8-1), the effect of treatment arm on the net change in the secondary efficacy measures will be analyzed using the same statistical model as in the primary efficacy analyses but with derived scores for each measure used as the dependent variables. In summary, data from all applicable visits will be analyzed with linear mixed models as described for the primary hypothesis. For most secondary efficacy measures, the data were collected at V1, V3 and V4, although the schedule differed for a few data forms as shown in Appendix A. Outcomes will be reported at each study visit using number of subjects, the mean \pm standard error, and 95% confidence limits of the mean, median, min, and max. Tests for significance of treatment group differences in the change from V1 to V4 will be evaluated with linear mixed models as described for the primary hypothesis. P-value testing for the main effects of treatment allocation will be reported for overall treatment effect and for the treatment effects at each study visit.

For secondary efficacy variables measured on an ordinal scale, the non-parametric signed-rank Wilcoxon test will instead be used to test for change between visits within each treatment group,

Version 3.0 Page 15 of 25

and there will be no adjustment for covariates. Patients' Global Impression of Change is the one secondary-efficacy measure that was not measured at V0 or V1, so the test for treatment group differences in that outcome will be evaluated using the Wilcoxon rank sum.

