11. CHANGES TO THE ANALYSES PLANNED IN THE PROTOCOL

No changes to the analyses planned in the protocol have been made.

Version 3.0 Page 21 of 25

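### GCPS Grade of Chronic Pain, an ordinal secondary outcome with a baseline, is tested only for change within each arm and never compared between propranolol and placebo

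*SAP*

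**What the plan says.** SAP Table 8-1 labels two secondary outcomes ordinal. One is PGIC, rated at Visits 3 and 4. The other comes from the GCPS: alongside two continuous scores, the table lists "one derived ordinal score (Grade of Chronic Pain) from the GCPS questionnaire". The schedule of events places the GCPS at Visits 1, 3 and 4, so the grade has a baseline.

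SAP 8.3.2 then assigns methods by type of variable:

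- Continuous variables and counts get the primary analysis's mixed model, with treatment effects tested between arms.
- For ordinal variables, "the non-parametric signed-rank Wilcoxon test will instead be used to test for change between visits within each treatment group", without covariates.
- PGIC has no Visit 0 or Visit 1 value, "so the test for treatment group differences in that outcome will be evaluated using the Wilcoxon rank sum".

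The secondary objective in SAP 2.1.2 is "To investigate the efficacy of extended-release propranolol compared with placebo using secondary endpoints". Protocol 11.1.2 hypothesises that, "compared with participants in the placebo-treated arm, participants in the propranolol-treated arm will have more favorable secondary endpoints". Protocol 11.4.2 states: "Linear mixed models will be used to evaluate effects of treatment group allocation on secondary efficacy variables", and refers to the SAP for details. SAP section 11 declares: "No changes to the analyses planned in the protocol have been made".

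**The concern.** A signed-rank test inside one arm asks whether that arm changed. The answer combines any drug effect with placebo response, natural course and regression to the mean. Some regression to the mean is likely here, because entry requires a pain rating of at least 30 at Visit 0 and again, from the diary, at Visit 1. The sample size table itself assumes a 9% fall in the pain index on placebo, so improvement without active drug is expected.

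The SAP treats P-values from secondary analyses as confirmatory in form: "The alpha level for determining significance will be set to 0.05 for all inference tests", and 8.3.2 applies the 0.05 threshold to secondary results without multiplicity correction. A within-arm P-value on the grade could therefore appear among the efficacy results as statistically significant when the arms do not differ. Conversely, if the drug works and placebo patients also improve, both arms may be significant and the drug effect goes unseen.

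**Working it through.** **Does any rule compare the arms on the grade?**

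1. Is it covered by the mixed model? No. That model is limited to continuous and count measures, and the sentence on treatment differences from Visit 1 to Visit 4 belongs to the same paragraph and names linear mixed models.
2. Is it covered by the ordinal rule? Yes, by its label in Table 8-1. That rule replaces the mixed model with a test inside each arm.
3. Is it covered by the PGIC exception? No. The stated reason is the absence of a baseline, and the grade has one at Visit 1.
4. Nothing else in the SAP compares the arms on the grade.

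**How far can the within-arm test mislead?** The documents give no planning figure for the grade, so there is none to reproduce and what follows is an illustration.

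Inputs from the protocol (11.2): 200 randomised 1:1; 10% loss, hence 90 per arm; planned net changes in the pain index of 270 (placebo) and 810 (drug); SD 1190. Standardised shifts: 270/1190 = 0.227 and 810/1190 = 0.681.

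Assumed: these shifts carry over to a latent score behind the grade; the correlation between visits is 0.5 or 0.7; the baseline grade follows one of three distributions (five levels at 20% each; five levels at 2/33/40/15/10%; four levels at 35/40/15/10%); tests are two-sided.

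*Approximate check.* With standardised change d and n per arm, p = Φ(d√n − 1.96) + Φ(−d√n − 1.96). At d = 0.227 and n = 90, d√n = 2.15 and p = 0.577. If the arms do not differ, the chance that the drug arm alone is significant is p(1 − p) = 0.577 × 0.423 = 0.244, and that exactly one arm is significant is 2p(1 − p) = 0.488.

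*Simulation*, 4,000 trials per setting, signed-rank with zeros dropped and ties corrected. Equal shift in both arms, so no drug effect; ranges span the assumed correlations and distributions:

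| Shift (SD) | n per arm | Drug arm P ≤ 0.05 | Drug arm only | Between-arm rank-sum on change |
|---|---|---|---|---|
| 0 | 90 | 4.4–5.4% | 4.3–5.1% | 4.3–5.1% |
| 0.1 | 90 | 12.3–16.9% | 11.1–14.0% | 4.5–5.4% |
| 0.227 | 90 | 42.2–64.0% | 21.6–25.3% | 4.4–5.2% |
| 0.3 | 90 | 64.5–87.8% | 10.8–24.3% | 4.5–5.3% |
| 0.227 | 100 | 45.7–69.9% | 21.1–25.7% | 4.6–5.3% |

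The first row shows that the signed-rank test is valid for its own null of no change in that arm. The other rows show that it does not test the null of no difference between arms.

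With the planned effect (0.681 against 0.227, n = 90), both arms are significant in 43.5–65.8% of trials and the drug arm alone in 34.2–56.4%. The between-arm test has 57.0–86.4% power.

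A separate simulation (five levels, other cut-points, correlation 0.6, 100 per arm, 2,000 runs) gave exactly one arm significant in 10%, 27%, 51% and 28% of runs at equal shifts of 0, 0.1, 0.2 and 0.3. The between-arm test rejected in 4.7–5.3%.

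**The case against.** **The outcome is small.** Protocol 7.1.14 describes the GCPS by two dimensions, intensity and disability. The SAP compares the two continuous GCPS scores between arms with covariate adjustment. The grade is a summary category that first appears in Table 8-1, among many supportive outcomes. This stands, and it limits the importance of the point. It does not supply a comparison for a variable that the SAP lists separately.

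**The protocol delegates the details.** Protocol 11.4 calls itself an overview and 11.4.2 points to the SAP, so a rank method for an ordinal variable could count as delegated detail. PGIC also leaves the mixed model. That is fair as to method. But the PGIC test keeps the treatment contrast and the rule for the grade drops it. Protocol 11.4.2 plans exactly that contrast, so losing it is more than a detail and sits badly with a declaration of no changes.

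**It may be a drafting slip.** The PGIC sentence reads as though the other ordinal measures also had a test of treatment differences. Possibly so, but no such test is named, and the text needs correcting either way.

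**The percentages describe a decision rule the SAP does not state.** Nowhere does it say that significance in the drug arm alone means efficacy, and the 42–64% are correct rejections of a real within-arm change. Applying 270 and 810 with 90 per arm also counts attrition twice, since the protocol's net changes already allow for 10% loss. Both points are right. The figures show what a reader could wrongly infer; they are not an error rate of a planned test. The attrition point hardly matters, as the row for 100 per arm shows.

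**Conclusion.** The concern holds. Followed as written, SAP 8.3.2 produces no randomised comparison for the GCPS grade, and its only stated test does not address the comparative secondary objective. This follows from the text and needs no numerical assumption.

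The scope is one of the two outcomes labelled ordinal. The simulated size of the problem depends on assumed grade distributions, visit correlations and carry-over of the pain-index shift, and should be read as an illustration. Within those assumptions, whenever both arms improve, the within-arm results are a poor guide to whether the arms differ, while a between-arm rank test stays near 5%. The point should be fixed before unmasking; it does not threaten the trial's main conclusion.

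**What to change.** In SAP 8.3.2, replace the within-arm test for Grade of Chronic Pain with one between-arm test at Visit 4, chosen and named before unmasking. Either of these would serve:

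- proportional-odds regression of the Visit 4 grade on treatment, site and Visit 1 grade; or
- a site-stratified rank-sum test on change from Visit 1 to Visit 4.

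Report changes within each arm descriptively, without P-values. Leave the PGIC rank-sum test as it is. Bring SAP 8.3.2 and section 11 into line with protocol 11.4.2: a test other than the mixed model for the grade should be listed in section 11 as a change.

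The cost is two SAP sentences and a few lines of code. The GCPS is already collected at Visits 1, 3 and 4, and the sample size does not change.

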## **4.4 Treatment Assignment Procedures**

### **4.4.1 Randomization Procedures**

Prior to randomization, the inclusion and exclusion criteria will be reviewed, and any participant who does not meet the criteria will be discontinued from the trial. Randomization will be stratified across 3 clinical sites for a total of 200 randomized participants. Within each site, participants will be randomized in a 1:1 ratio of active drug to placebo within prespecified blocks. Randomization will be accomplished by a web-based randomization system developed and maintained by the data coordinating center. At the time of randomization, study staff, who will remain blinded to treatment assignment, will access the system, enter the participant's study identification number, and verify that the participant is eligible for randomization. The system will assign a randomization code that will indicate to the pharmacy the participant's treatment assignment.

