### **7.1.14 Outcome Measure Questionnaires**

The questionnaires that will be utilized are listed in the Schedule of Events (Appendix A) and are briefly described below. Copies of the questionnaires are reproduced in the attachments. Several questionnaires are self-administered, and others will be administered by trained study staff. For outcome measure questionnaires, responses will be recorded on paper Teleform case report forms, which will be scanned as described in the MOP.

Short-Form McGill Pain Questionnaire. This questionnaire consists of 15 descriptors (11 sensory, 4 affective) which are rated on an intensity scale as 0 (“none”), 1 (“mild”), 2 (“moderate”), or 3 (“severe”).

Graded Chronic Pain Scale (GCPS). The GCPS comprises 7 items and assesses 2 dimensions of pain: pain intensity and pain-related disability.

Fibromyalgia Questionnaire. This questionnaire assesses the ACR criteria for fibromyalgia (1990) and includes pain-related questions and manikin drawings of participant pain location.

Short Form 12 Health Survey Version 2 (SF-12 v2). The SF-12 v2 is a briefer measure of health-related quality of life derived by using 12 items from the original Short Form 36 instrument. This questionnaire produces 2 scores: a mental health composite score and a physical health composite score.

Patient Global Impression of Change (PGIC). The PGIC is a participant-rated instrument that measures change in participant's overall status on a scale ranging from 1 ("very much improved") to 7 ("very much worse"). The PGIC is based on the Clinical Global Impression of Change, which is a validated scale.

Jaw Functional Limitation Scale. This 20-item instrument measures limitations across 3 domains: mastication (6 items), vertical jaw mobility (4 items), and verbal and emotional expression (8 items). Two items are not scored as part of these 3 subscales. A degree of limitation is rated on a 0-10 scale from 0 ("no limitation") to 10 ("severe limitation").

Perceived Stress Scale. This questionnaire assesses 14 sources of stress and produces an overall perceived stress rating.

Hospital Anxiety and Depression Scale. This 14-item instrument evaluates anxiety and depression.

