2.5 Treatment Group Assignments or Randomization

At the Randomization and Titration Visit, participants will be randomized 1:1 to propranolol or placebo. Randomization will be stratified by site and conducted within blocks to insure equal

Version 3.0 Page 6 of 25

numbers of participants per arm. Randomization will be accomplished by a web-based randomization system developed and maintained by the Data Coordinating Center (DCC).

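### PGIC is compared between arms by a rank-sum test that ignores the site strata and the Visit 1 pain index: valid, but it loses some power if either predicts PGIC

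*SAP*

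**What the plan says.** PGIC is a single seven-point rating that, in Protocol 7.1.14, "measures change in participant's overall status on a scale ranging from 1" (very much improved) to 7 (very much worse). Global impression of change is named in the secondary objective (Protocol 2.4.2). SAP Table 8-1 lists it as an efficacy variable: "The ordinal rating of change, measured at the subject's visits 3 and 4, will be reported as two secondary outcome variables".

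SAP 8.3.2 tests ordinal secondary variables within each arm by the signed-rank test, "and there will be no adjustment for covariates". It then makes an exception for PGIC, because PGIC is not measured at V0 or V1: "so the test for treatment group differences in that outcome will be evaluated using the Wilcoxon rank sum". That sentence names no strata, no covariates and no visit. SAP 8.3 sets the threshold: "The alpha level for determining significance will be set to 0.05 for all inference tests".

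On allocation, SAP 2.5 says: "Randomization will be stratified by site and conducted within blocks". Protocol 4.4.1 agrees: "Within each site, participants will be randomized in a 1:1 ratio of active drug to placebo within prespecified blocks".

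The primary mixed model and the responder logistic models (SAP 8.3.1), and the models for days on rescue medication or over-the-counter analgesics (SAP 8.3.2), all include site and the Visit 1 mean pain index. Continuous and count secondary measures use the same model as the primary analysis.

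**The concern.** PGIC is the one between-arm efficacy comparison that takes no account of the randomization strata or of any baseline value.

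The missing baseline rating does not explain this. It rules out a change score, but both site and the Visit 1 pain index are available. The SAP already does the same thing elsewhere: the model for days on rescue medication contains no baseline value of that outcome, yet it adjusts for exactly these two variables.

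What is at stake is efficiency on a named secondary endpoint, through two separate routes:
- **Site.** Blocked 1:1 allocation within site removes site differences from the true variance of the arm comparison, but an unstratified test still counts them in its estimated variance. If site predicts PGIC, the test is conservative.
- **Visit 1 pain index.** The design does not balance this variable, so ignoring it leaves the size correct. If it predicts PGIC, ignoring it leaves removable noise in the comparison.

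**Working it through.** **1. The plan's own figure.** There is none for PGIC. The 94% and 61% powers (Protocol 11.2, SAP 2.6) concern the pain index and the haplotype interaction.

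**2. Inputs from the documents.** N = 200, three sites, 1:1 within site, seven ordered categories, alpha 0.05 (read as two-sided), 10% loss to follow-up (Protocol 11.2).

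**3. Assumptions, not in the documents.** A normal latent outcome is cut into seven categories. The treatment shift is 0.40 SD (site runs) or 0.45 SD (Visit 1 index runs). Site means are −s, 0 and +s SD in near-equal sites. The Visit 1 index has latent coefficient b (residual SD units per SD of the index).

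**4. Site alone.** The share of variance due to site is R² = (2s²/3) / (1 + 2s²/3). For s = 0.2 this is 0.0267/1.0267 = 2.6%. Simulation used 40,000 trials per row and sites of 66/66/68:

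| s | R² | Rank-sum size | Rank-sum power | van Elteren power | Loss (points) |
|---|---|---|---|---|---|
| 0 | 0% | 0.050 | 76.3% | 76.1% | none |
| 0.1 | 0.7% | 0.049 | 76.1% | 76.0% | none |
| 0.2 | 2.6% | 0.047 | 75.5% | 76.0% | 0.5 |
| 0.3 | 5.7% | 0.043 | 74.4% | 76.1% | 1.7 |
| 0.5 | 14% | 0.033 | 71.3% | 76.2% | 4.9 |

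The van Elteren size stays at about 0.049 to 0.050. Other layouts give the same pattern. At s = 0.5, sites of 100/60/40 give 71.7% against 76.0%, and N = 180 gives 66.1% against 71.3%.

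*Analytic check.* The unstratified statistic is the stratified one multiplied by √(1 − R²). So size = 2[1 − Φ(1.96/√(1 − R²))] and power = Φ(δ − 1.96/√(1 − R²)), where δ is the noncentrality of the stratified test. At R² = 5%, 1.96/0.9747 = 2.011 and the size is 0.044. With 80% stratified power, δ = 2.802 and unstratified power is Φ(0.791) = 78.5%. At R² = 10% it is 76.9%.

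**5. Visit 1 index alone.** Here R² = b²/(1 + b²), which is 8.3% at b = 0.3 and 20% at b = 0.5. The matching correlations with latent PGIC are 0.29 and 0.45. Simulated power (3,000 trials per cell, Monte Carlo error about 0.7 point, 200 randomized, 10% missing, no site effect), rank-sum against rank ANCOVA on site and the index:
- b = 0.3: 78.2% against 81.4%; a second run gave 79% against 82%.
- b = 0.5: 72.2% against 79.4%; a second run gave 73% against 82%.
- b = 0: 81.5% against 81.4%.

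The loss is therefore about 3 to 9 points.

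*Analytic check.* Rank-sum power ≈ Φ(δ√(1 − R²) − 1.96). With adjusted power of 81.4%, δ = 2.853. At b = 0.3 this gives Φ(2.853 × 0.958 − 1.96) = Φ(0.772) = 78.0%. At b = 0.5 it gives Φ(2.853 × 0.894 − 1.96) = Φ(0.592) = 72.3%.

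**6. Both together.** With a modest site effect (about 4% of variance), the rank-sum gives 77.9% against 81.7% at b = 0.3, and 71.5% against 80.4% at b = 0.5.

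**The case against.** The choice is prespecified, gives a reason, and yields a valid test. SAP 8.3.2 treats secondary analyses as supportive and applies no multiplicity correction, and the plan claims no power for PGIC. A rank-sum test also avoids the proportional-odds assumption. All of this stands, and it limits the weight of the point.

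Three stronger readings are tempting, and the documents do not support them.

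- *A reader might infer that stratified randomization by itself makes the test conservative.* It does not: site must also predict PGIC. With no site effect the simulated size is 0.050 and nothing is lost.
- *A reader might infer a site-driven loss of ten points or more.* In the same simulation, a loss of 11.5 points (63.9% against 75.4%) needs site to explain 27% of the variance. Even the 14% row puts the extreme sites 1.0 SD apart, which is 2.5 times the assumed treatment shift of 0.40 SD. No document reports a site difference in PGIC.
- *A reader might infer a validity problem.* Ignoring a stratification factor or a baseline covariate here does not raise the Type I error materially above 0.05.

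The Visit 1 index figures are also conditional: the documents give no correlation between that index and PGIC.

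The objection does not show that the unadjusted test is the better choice. Where neither factor matters, stratifying or adjusting costs at most about 0.2 point; where either matters, it gains.

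**Conclusion.** The point holds as a minor matter of efficiency and consistency. The PGIC comparison departs from the SAP's other between-arm efficacy models, and the stated reason does not require that departure.

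The size depends on effects that the documents do not give. Under the assumptions above, the loss from ignoring site runs from nothing (0 to 0.7% of variance) through 0.5 point (2.6%) and 1.7 points (5.7%) to about 5 points (14%). Ignoring the Visit 1 index costs about 3 to 9 points for b between 0.3 and 0.5. If neither predicts PGIC, nothing material is gained or lost. The primary analysis is untouched.

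**What to change.** Amend the PGIC sentence in SAP 8.3.2, before unblinding, to name Visit 4 as the main PGIC comparison and to use one of the following:

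- **van Elteren test stratified by site.** This is the smallest change and recovers the site component only.
- **Rank ANCOVA or proportional-odds model at Visit 4 with site and the Visit 1 mean pain index.** These are the covariates of the SAP's own responder model, and this option addresses both components. If the proportional-odds model is chosen, report the odds ratio with its 95% confidence interval and check the proportional-odds assumption. The adjusted method simulated above is the rank ANCOVA; the proportional-odds model was not simulated.

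The same edit should say how a missing Visit 4 rating is handled. SAP 8.1 relies on the mixed model, which does not cover a rank test, and a participant rated only at Visit 3 adds nothing to any Visit 4-only comparison. A repeated-measures ordinal model over Visits 3 and 4 would use those ratings; it is optional, and its performance was not evaluated here.

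The cost is a short change of SAP text and standard SAS code. No new data are needed.
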